3.3.3 Women of Childbearing Potential

A Woman of Childbearing Potential (WOCBP) is defined as any female who has experienced menarche and who has not undergone surgical sterilization (hysterectomy or bilateral oophorectomy) and is **not** postmenopausal. Menopause is defined as 12 months of amenorrhea in a woman over age 45 years in the absence of other biological or physiological causes. In addition, females under the age of 55 must have a serum follicle stimulating hormone, (FSH) level > 40 mIU/mL to confirm menopause.

*Females treated with hormone replacement therapy, (HRT) are likely to have artificially suppressed FSH levels and may require a washout period in order to obtain a physiologic FSH level. The duration of the washout period is a function of the type of HRT used. The duration of the washout period below are suggested guidelines and the investigators should use their judgment in checking serum FSH levels. If the serum FSH level is > 40 mIU/ml at any time during the washout period, the woman can be considered postmenopausal:

- 1 week minimum for vaginal hormonal products, (rings, creams, gels)
- 4 week minimum for transdermal products
- 8 week minimum for oral products

Other parenteral products may require as long as 6 months.

3.4 Concomitant Treatments

All medications taken within 28 days before the administration of study drug and all concomitant therapy administered during the study will be recorded on the relevant CRF, along with the reasons for and details of therapy use.

3.4.1 *Prohibited and/or Restricted Treatments*

- 1) Concurrent chemotherapy, hormonal therapy, immunotherapy regimens, or radiation therapy, standard or investigational. Exceptions include:
 - a) Palliative or supportive care may be offered to all subjects.
 - b) Palliative/therapeutic therapies (e.g., focal radiotherapy for pain or bone metastases, thoracocentesis or paracentesis for comfort) may be administered after consultation with the Medical Monitor.
 - c) Palliative radiation therapy for bone metastases is permitted, but subjects should not receive study treatment during radiation and must meet re-treatment criteria prior to resuming treatment.
 - d) Treatment of isolated symptomatic lesions by local surgery is permitted for palliative or potentially curative management at any time. All interventions should be discussed in advance with the BMS Medical Monitor. All tumor tissue that is not required for clinical pathology will be sent to BMS.
 - e) A new biopsy will not be required for resuming re-treatment in the setting of interrupted active treatment for local palliative therapies, although it is encouraged, if considered safe by the investigator. All tumor tissue that is not required for clinical pathology will be sent to BMS.
- 2) Use of growth factors including, but not limited to, granulocyte colony stimulating factor (G-CSF), granulocyte macrophage colony stimulating factor (GM-CSF), or erythropoietin stimulating agents are not permitted, unless deemed necessary by investigator and discussed with medical monitor.
- 3) Use of systemic corticosteroids at > 10 mg daily prednisone equivalent, unless required for the treatment of infusion reactions, other adverse events, or for palliation as determined by the investigator.
- 4) Use of RANKL therapy unless required for management of osteolytic bone lesions, other adverse events or for palliation and after a discussion between the investigator and the medical monitor. Since RANKL therapy is a recognized immune modulator, **discussion must occur before starting any patient on RANKL therapy.**
- 5) Use of bisphosphate therapy, unless required for management of osteolytic bone lesions, adverse events or for palliation and after a discussion between the investigator and the medical monitor. Since bisphosphonates are recognized as immune modulators, **discussion must occur before starting any patient on bisphosphonate therapy.**
- 6) Steroids must not be given as prophylactic anti-emetic therapy.
- 7) Use of herbal remedies is not permitted

Use of prescription and over-the-counter medications (except medications from categories outlined above) is permitted at the discretion of the Investigator and must be recorded on CRF.

3.4.2 Other Restrictions and Precautions

None

3.4.3 Permitted Therapy

Subjects are permitted the use of topical, ocular, intranasal, intra-articular, and inhalational corticosteroids (with minimal systemic absorption). Immunosuppressive doses (e.g., prednisone > 10 mg/day or equivalent) and/or physiologic replacement doses of systemic corticosteroids (e.g., prednisone ≤ 10 mg/day) are permitted in the context of treating adverse events. A brief course of corticosteroids for prophylaxis (e.g., contrast dye allergy) or for treatment of non-autoimmune conditions (e.g., delayed-type hypersensitivity reaction caused by a contact allergen) is permitted.

Prophylactic anti-emetics, with the exception of steroids, may be administered at the discretion of the treating physician before any doses of study drug.

Use of the seasonal killed influenza vaccine during therapy is permitted without restriction. However, influenza vaccines containing live attenuated virus (Flumist®) or other clinically indicated vaccinations for infectious diseases (killed or attenuated, e.g., Pneumovax®, varicella, MMR, etc) may be permitted, but must be discussed with the Sponsor's Medical Monitor and may require a study drug washout period prior to and after administration of the vaccine.

3.5 Discontinuation of Subjects From Treatment

3.5.1 Permanent Discontinuation Criteria of Subjects from Treatment

Subjects MUST PERMANENTLY discontinue investigational product (and non-investigational product at the discretion of the investigator) for any of the following reasons:

- Withdrawal of informed consent (subject's decision to withdraw for any reason)
- Any clinical adverse event (AE), laboratory abnormality or intercurrent illness which, in the opinion of the investigator, indicates that continued participation in the study is not in the best interest of the subject as per [Section 4.3.5](#)
- Pregnancy
- Termination of the study by Bristol-Myers Squibb (BMS)
- Loss of ability to freely provide consent through imprisonment or involuntary incarceration for treatment of either a psychiatric or physical (e.g., infectious disease) illness
- Subjects should discontinue study therapy upon evidence of further disease progression, defined as an additional 10% or greater increase in tumor burden volume from the time of initial progression (including all target lesions and new measurable lesions), as per [Section 4.3.8](#)
- Clinical deterioration while receiving active study therapy.
- Inability to comply with the protocol

All subjects who discontinue should comply with protocol specified follow-up procedures as outlined in [Section 3.1](#). The only exception to this requirement is when a subject withdraws consent for all study procedures or loses the ability to consent freely (i.e., is imprisoned or involuntarily incarcerated for the treatment of either a psychiatric or physical illness).

If study treatment is discontinued prior to the subject's completion of the study, the reason for the discontinuation must be documented in the subject's medical records and entered on the appropriate case report form (CRF) page.

3.6 Post Treatment Study Follow-up

Subjects who discontinue study treatment may continue to be followed. Please refer to [Section 3.1](#) and Tables in [Section 5.1](#) for details.

3.6.1 Withdrawal of Consent

Subjects who request to discontinue study treatment will remain in the study and must continue to be followed for protocol specified follow-up procedures. The only exception to this is when a subject specifically withdraws consent for any further contact with him/her or persons previously authorized by subject to provide this information. Subjects should notify the Investigator of the decision to withdraw consent from future follow-up **in writing**, whenever possible. The withdrawal of consent should be explained in detail in the medical records by the Investigator, as to whether the withdrawal is from further treatment with study drug only or also from study procedures and/or post treatment study follow-up, and entered on the appropriate CRF page. In the event that vital status (whether the subject is alive or dead) is being measured, publicly available information should be used to determine vital status only as appropriately directed in accordance with local law.

3.6.2 Lost to Follow-Up

All reasonable efforts must be made to locate subjects to determine and report their ongoing status. This includes follow-up with persons authorized by the subject as noted above. Lost to follow-up is defined by the inability to reach the subject after a minimum of three documented phone calls, faxes, or emails as well as lack of response by subject to one registered mail letter. All attempts should be documented in the subject's medical records. If it is determined that the subject has died, the site will use permissible local methods to obtain the date and cause of death.

If Investigator's use of third-party representative to assist in the follow-up portion of the study has been included in the subject's informed consent, then the Investigator may use a BMS-retained third-party representative to assist site staff with obtaining subject's contact information or other public vital status data necessary to complete the follow-up portion of the study. If after all attempts, the subject remains lost to follow-up, then the last known alive date as determined by the investigator should be reported and documented in the subject's medical records.

4 TREATMENTS

All protocol-specified investigational and non-investigational products are considered study drug.

4.1 Study Treatments

Treatment administration for nivolumab and ipilimumab (a ± 2 -day window will be allowed):

Table 4.1-1: Treatment Administration

Cohort/Arm	Dose	Infusion Time
1 and 2	3 mg/kg nivolumab every 2 weeks	60 minutes
A	1 mg/kg nivolumab + 3 mg/kg ipilimumab every 3 weeks x 4 doses and then 3 mg/kg nivolumab every 2 weeks	Part 2: nivolumab 60 minutes + 30 minutes break ipilimumab 90 minutes and then nivolumab 60 minutes
		Part 3: nivolumab 30 minutes + 30 minutes break ipilimumab 30 minutes and then nivolumab 30 minutes
B	3 mg/kg nivolumab every 2 weeks	30 minutes
D	1 mg/kg nivolumab + 3 mg/kg ipilimumab every 3 weeks x 4 doses and then 3 mg/kg nivolumab every 2 weeks	nivolumab 30 minutes + 30 minutes break ipilimumab 30 minutes and then nivolumab 30 minutes
E	3 mg/kg nivolumab every 2 weeks	30 minutes

Table 4.1-2: Product Description

Product Description and Dosage Form	Potency	Primary Packaging (Volume)/ Label Type	Secondary Packaging (Qty) /Label Type	Appearance	Storage Conditions (per label)
BMS-936558-01 Solution for Injection	100 mg (10mg/mL)	10 mL/ open label	10 vials per box/ open labels	Colorless to pale yellow, clear to opalescent solution; may contain particles	Store Refrigerated, 2-8° C (36-46 F) Protect from light and freezing.
Ipilimumab Solution for Injection	200 mg (5 mg/mL)	40 mL per vial/Open- label	4 vials per carton/Open-label	Clear, colorless to pale yellow liquid. May contain particles	2 to 8°C. Protect from light and freezing.

4.1.1 Investigational Product

An investigational product, also known as investigational medicinal product in some regions, is defined as follows:

A pharmaceutical form of an active substance or placebo being tested or used as a reference in a clinical study, including products already with a marketing authorization but used or assembled (formulated or packaged) in a way different from the authorized form, or used for an unauthorized indication, or when used to gain further information about the authorized form.

The investigational product should be stored in a secure area according to local regulations. It is the responsibility of the investigator to ensure that investigational product is only dispensed to study subjects. The investigational product must be dispensed only from official study sites by authorized personnel according to local regulations.

In this protocol, the investigational products are: nivolumab and ipilimumab

The sites will be responsible to procure IV bags, diluents, and micron in-line filters (ie 0.2/ 0.22 micron; see current nivolumab and ipilimumab Investigator Brochure for required filter details)

4.1.2 Non-investigational Product

Other medications used as support or escape medication for preventative, diagnostic, or therapeutic reasons, as components of the standard of care for a given diagnosis, may be considered as non-investigational products.

In this protocol, non-investigational product(s) are not applicable.

4.1.3 Handling and Dispensing

The product storage manager should ensure that the study drug is stored in accordance with the environmental conditions (temperature, light, and humidity) as determined by the Sponsor. If concerns regarding the quality or appearance of the study drug arise, do not dispense the study drug and contact the Sponsor immediately.

4.1.4 Nivolumab Vial Storage

The product storage manager should ensure that the study drug is stored in accordance with the environmental conditions (temperature, light, and humidity) as determined by the sponsor. If concerns regarding the quality or appearance of the study drug arise, do not dispense the study drug. Contact the sponsor immediately. Nivolumab vials must be stored in the refrigerator at 2-8°C, protected from light and freezing. If stored in a glass front refrigerator, vials should be stored in the carton. Recommended safety measures for preparation and handling of nivolumab include laboratory coats and gloves.

After nivolumab has been prepared for administration, the total storage time (combination of refrigeration and room temperature exposure) is not to exceed 24 hours. For details on prepared drug storage and use time under room temperature/light and refrigeration, please refer to the

current nivolumab Investigator Brochure.⁴⁸ Care must be taken to assure sterility of the prepared solution as the product does not contain any anti-microbial preservative or bacteriostatic agent.

4.1.5 Ipilimumab Vial Storage

For ipilimumab storage and administration instructions, please refer to the ipilimumab IB.

4.1.6 Study Drug Administration

Nivolumab is to be administered as an approximate 60 minute IV infusion in Parts 1 and 2, using a volumetric pump with a 0.2/0.22 micron in-line filter at the protocol-specified doses. It is not to be administered as an IV push or bolus injection. At the end of the infusion, flush the line with a sufficient quantity of normal saline (per institutional standard of care). Details regarding the mixing and concentrations of the dose (preparation) and administration will be found in the current Investigator Brochure for nivolumab.⁴⁸

Ipilimumab is to be administered as an approximate 90-minute IV infusion in Parts 1 and 2, using a volumetric pump with a 0.2 to 1.2 micron in-line filter at the protocol-specified dose. Care must be taken to assure sterility of the prepared solutions, since the drug product does not contain any antimicrobial preservatives or bacteriostatic agents. Please refer to the ipilimumab IB for further details regarding preparation/administration.

In Parts 3 and 4 of the study, the infusion times for nivolumab and ipilimumab will be shortened to 30 minutes each.

When both study drugs are to be administered on the same day, separate infusion bags and filters must be used for each infusion. Nivolumab is to be administered first. The nivolumab infusion must be promptly followed by a saline flush to clear the line of nivolumab before starting the ipilimumab infusion. The second infusion will always be the ipilimumab study drug, and will start no sooner than 30 minutes after completion of the nivolumab infusion and after the post-nivolumab pharmacokinetic blood sample is drawn.

4.2 Method of Assigning Subject Identification

CA209038 is an open-label study. All enrolled subjects will be assigned a subject number, starting with 00001 and increasing sequentially with each additional enrolled subject. The subject number will be assigned by the Sponsor via IVRS once the subject signs the informed consent form. Each subject will then be identified by a distinct patient identification number (PID) which is comprised of the site number and the subject number. The Investigator or designee will register the subject following the enrollment procedures established by BMS. The following information is required for registration:

- Date of birth
- Gender
- Diagnosis
- Date of Informed Consent
- Planned date of 1st dose

Subjects will undergo screening evaluations to determine eligibility within 28 days prior to dosing. The investigative site will contact the Sponsor via IVRS for treatment assignment once a subject is determined to be eligible for enrollment. Enrolled subjects meeting all eligibility criteria will be assigned to Cohort 1 or 2 depending on prior anti-CTLA4 therapy status. After Amendment 04, enrolled subjects meeting all eligibility criteria will be assigned to Arm A for Part 2. After the optimal timing of the biopsy has been determined in Part 2 then, enrolled subjects meeting all eligibility criteria will be randomly assigned to Arms A or B in a 2:1 ratio in Part 3. In parallel, enrolled subjects meeting all eligibility criteria will be randomly assigned to Arms D or E in a 1:1 ratio in Part 4.

Subjects who do not have both pre-treatment and on-treatment biopsy will be replaced. Subjects in Arms D and E may undergo optional biopsies, especially if they have lesions in locations other than the brain. Subjects in Arms D and E will not be replaced. Replacement subjects will receive the same treatment but will be assigned a new subject number.

Specific instructions regarding enrollment and randomization will be provided to the investigational sites in their training materials.

4.3 Selection and Timing of Dose for Each Subject

As described in [Section 4.2](#), subjects will be assigned to a cohort/arm in the order they enter the study. The subjects enrolled prior to Amendment 04 will be assigned a patient identification number (PID) by IVRS and placed into 1 of 2 dose cohorts based on whether they have had prior anti-CTLA4 treatment. Subjects enrolled after Amendment 04 will be assigned a patient identification number (PID) by IVRS and placed into Arms A, B, D or E.

4.3.1 Dose Modifications

There will be no actual dose adjustments allowed for nivolumab or ipilimumab except for weight changes (an increase or decrease of $\geq 10\%$ in weight) at the beginning of each cycle.

4.3.2 Intrasubject Dose Escalation

No intrasubject dose escalation will be allowed

4.3.3 Dose Reductions

Nivolumab and ipilimumab dose reductions are not permitted in this study.

4.3.4 Dose Delay Criteria

Study drug administration should be interrupted and increased monitoring of subjects should ensue if any of the following drug related adverse event(s) occurs:

- Any persistent grade ≥ 2 non laboratory non-skin drug related adverse event except for fatigue and weakness
- Any grade ≥ 2 endocrine drug-related adverse event
- Any grade ≥ 3 skin drug related adverse event

- Any Grade ≥ 3 drug-related laboratory abnormality (except lymphopenia, asymptomatic lipase or amylase increases, or any electrolyte abnormality without any clinical sequelae that is either spontaneously reversible or resolves with clinical management to grade 2 or less within 72 hours)
- ALT or AST $> 3X$ ULN (treatment may resume when the AE resolves to Grade 1)
- Patients with pre-existing neurologic or ophthalmologic anti-CTLA4 related adverse event who develop clinical symptoms leading to a 1 grade drug related shift (i.e. grade 1 to grade 2)
- Any AE, laboratory abnormality or inter-current illness which, in the judgment of the investigator, warrants skipping the dose of study medication

If dose delay is necessary, both nivolumab and ipilimumab must be delayed until treatment can resume. If a delay prevents subsequent infusion of ipilimumab, the dose of ipilimumab should be replaced as soon as possible. At least 19 days must elapse between the replacement dose of ipilimumab and the administration of the next dose of the combination.

The occurrence of clinically meaningful drug related AEs requires early recognition and prompt intervention. Management algorithms are available for suspected pulmonary, gastrointestinal, hepatic, renal, endocrine, neurological and skin toxicities. The recommendation is to follow the nivolumab IB adverse event algorithm. The algorithms can also be found on [Appendix 4](#).

4.3.5 Study Drug Discontinuation Criteria due to Adverse Event(s)

Study drug administration must be discontinued if at least one of the following drug related adverse event(s) occurs:

- Any \geq Grade 2 eye pain or reduction of visual acuity that does not respond to topical therapy and does not improve to Grade 1 severity within 2 weeks of starting therapy OR requires systemic treatment;
- Any \geq Grade 3 non laboratory drug-related adverse event with the exception of fatigue, and endocrine drug related AEs which are stable with hormone replacement therapy
- Any \geq Grade 3 bronchospasm, hypersensitivity reaction, or infusion reaction;
- Any patient that experiences any grade allergic/infusion reaction while receiving study drug at a slower infusion rate and/or with premedication due to a prior allergic/infusion reaction
- Any drug-related Grade 4 laboratory abnormalities, (except lymphopenia, asymptomatic lipase or amylase increases, or any electrolyte abnormality without any clinical sequelae that is either spontaneously reversible or resolves with clinical management to grade 2 or less within 72 hours)

- Hepatotoxicity as evidenced by any of the following:
 - AST or ALT > 5 - 10x ULN for >2 weeks
 - AST or ALT > 10 ULN
 - Total bilirubin > 5 x ULN
 - Concurrent AST or ALT > 3 x ULN and total bilirubin > 2 ULN (potential Hy's Law case)
- Any adverse event, laboratory abnormality or intercurrent illness, which in the judgment of the Investigator, presents a substantial clinical risk to the subject
- All adverse events that meet discontinuation criteria, as well as any Grade 3 or 4 infusion reactions must be reported to BMS, within 24 hours using the rapid notification procedures described in [Section 6.1.1](#).

Subjects who experience AEs that require discontinuation while receiving both nivolumab and ipilimumab may be allowed to continue therapy with nivolumab only if deemed in their best interest by both the PI and the BMS medical monitor. This will be decided on a case by case basis and will require convincing evidence that the benefit outweighs the risk.

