4.3.6 Criteria to Resume Treatment with Study Drug

Subjects may resume treatment with study drug when the drug-related AE(s) resolve(s) to Grade 1 or baseline value. Subjects must be re-treated within 6 weeks from the previous dose. For selected patients who are assessed to be deriving clinical benefit from treatment or for patients where resumption of therapy is delayed, re-initiation of therapy may be delayed even further on a case-by-case basis in consultation with the Sponsor.

In the case of endocrine-related AEs, hormone replacement therapy may be utilized to restore physiologic function and to permit retreatment with nivolumab. If this is not possible, the subject must be discontinued from study therapy.

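### Every drug-related Grade 3 or higher skin event meets both the delay rule in Protocol 4.3.4 and the mandatory stop in 4.3.5, and the visible text does not say how the two fit together

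*Protocol*

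**What the plan says.** Three consecutive protocol sections govern a drug-related adverse event.

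- **4.3.4 (delay).** "Study drug administration should be interrupted and increased monitoring of subjects should ensue" when a listed event occurs. The general trigger for non-laboratory events starts at Grade 2 but excludes skin. Skin has its own line: "Any grade ≥ 3 skin drug related adverse event".
- **4.3.5 (stop).** "Study drug administration must be discontinued if at least one of the following drug related adverse event(s) occurs". One listed criterion is, at Grade 3 or above, any "non laboratory drug-related adverse event with the exception of fatigue, and endocrine drug related AEs which are stable with hormone replacement therapy". Skin is not among the exceptions.
- **4.3.6 (resume).** "Subjects may resume treatment with study drug when the drug-related AE(s) resolve(s) to Grade 1 or baseline value". The section does not exclude events that met a 4.3.5 criterion.

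Two other provisions bear on the point. Section 3.5.1, under the instruction that "Subjects MUST PERMANENTLY discontinue investigational product", refers to 4.3.5 for adverse events, but through the investigator's opinion. Section 4.3.5 also gives one route onward after a required stop: subjects whose event arose "while receiving both nivolumab and ipilimumab may be allowed to continue therapy with nivolumab only if deemed in their best interest". Both the investigator and the medical monitor must agree, case by case.

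**The concern.** Section 4.3.4 takes skin out of the Grade 2 rule and gives it a higher threshold of its own. A reader will naturally take that to mean that a Grade 3 skin event is to be held and then, on recovery, resumed under 4.3.6. Section 4.3.5 says that the same event ends treatment.

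What is at stake is patient handling. In a multicenter study, one site could stop a subject permanently while another restarts drug after the same event, and each could point to a section of the protocol. The second site would have re-exposed a subject for whom the protocol requires discontinuation.

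**Working it through.** No figure in the plan depends on this point, so the check is a comparison of the rules.

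**Step 1: is the overlap complete?** The delay trigger covers events that are drug-related, skin, and Grade 3 or higher. The stop criterion covers events that are drug-related, non-laboratory, and Grade 3 or higher, less fatigue and less endocrine events stable on hormone replacement. A skin event is non-laboratory and is neither fatigue nor endocrine. Every event in the first set is therefore in the second. Both rules require drug-relatedness, so the delay line cannot be read as a holding step while attribution is settled.

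**Step 2: is this just the usual overlap?** The 4.3.4 triggers are lower bounds, so some overlap with 4.3.5 at higher grades is expected. The test is whether each specific trigger keeps a range in which only a delay applies.

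| 4.3.4 trigger | Where 4.3.5 takes over | Left for delay only |
|---|---|---|
| Persistent non-laboratory, non-skin, Grade 2 up | Grade 3 up | Grade 2 |
| Endocrine, Grade 2 up | Grade 3 up, unless stable on hormone replacement | Grade 2, and higher grades once stable |
| Laboratory, Grade 3 up | Grade 4 | Grade 3 |
| ALT or AST above 3 × ULN | Above 5 to 10 × ULN for over 2 weeks, or above 10 × ULN | Above 3 and up to 5 × ULN, if no bilirubin criterion is met |
| Pre-existing neurologic or ophthalmologic event, one-grade shift | Grade 3 up | Grade 1 to 2 shift |
| Skin, Grade 3 up | Grade 3 up | None |

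The separate 4.3.5 criteria for eye events and infusion reactions remove some cases from these ranges but empty none of them. Skin is the only specific trigger with nothing left.

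**Step 3: does any visible text set precedence?** Sections 3.5.1, 4.3.4, 4.3.5, 4.3.6 and 4.3.9 contain no sentence that does. The nearest guidance is the strength of the verbs: *should* in 4.3.4, *must* in 4.3.5, *may* in 4.3.6. Section 4.3.4 also sends sites to the nivolumab Investigator Brochure algorithm, reproduced in Appendix 4. The visible skin footnote there orders permanent discontinuation when SJS or TEN is diagnosed. The skin figure itself is not shown and the brochure is not available, so this search is limited to the visible text.

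**Step 4: who has the nivolumab-only route?** It requires that the event arose on both drugs. Cohorts 1 and 2 and Arms B and E, about 40 + 40 + 10 + 10 = 100 of the planned 150, never have it. Arm A (20 in Part 2 and 20 in Part 3) and Arm D (10), about 50 in all, have it during combination dosing. These numbers show whom the route covers; they do not estimate how many subjects would be affected.

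**The case against.** The strongest reply is that the rules do not conflict: a site that interrupts drug under 4.3.4 and then discontinues under 4.3.5 has obeyed both. The verbs point the same way. If 4.3.6 allowed general resumption after a stop criterion, the nivolumab-only paragraph would have little purpose. On this view the skin line is merely redundant. As a reading of intent this is the better one, and it stands. It remains an inference, however, and it leaves a separately drafted threshold with no function for a subject on nivolumab alone, which invites the other reading.

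A second reply is that the sponsor would learn of the event anyway: "All adverse events that meet discontinuation criteria, as well as any Grade 3 or 4 infusion reactions must be reported to BMS", within 24 hours. That duty attaches to meeting the criterion, so it holds under either reading. It is a real safeguard, although it relies on the site recognising that a stop criterion was met.

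Several stronger claims are tempting and are not supported:

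- *That the protocol gives no governing text anywhere.* The Appendix 4 skin figure and the brochure algorithm are unseen.
- *That the study's results are distorted.* SAP 7.6.3 identifies discontinuation events by the action taken, so the tables there and in SAP 7.6.4 record what was actually done.
- *That the nivolumab-only route closes at Week 12.* Section 4.3.4 provides for replacing a delayed ipilimumab dose, and 4.3.6 allows re-treatment up to 6 weeks from the previous dose, or later in consultation with the sponsor. Combination dosing can therefore run past Week 12.

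**Conclusion.** The point holds as a drafting defect in a patient-safety rule. The skin delay trigger lies wholly inside the mandatory stop rule. Discontinuation is the better reading, but a site following 4.3.4 and then 4.3.6 could reach the opposite result.

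The consequence is confined to consistent handling of subjects with a drug-related Grade 3 or higher skin event. The documents give no rate for such events and no basis for guessing how many would be resumed, so the number affected is unknown. No endpoint, precision figure or sample size changes.

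The conclusion rests on the visible text. If the Appendix 4 skin figure or the brochure states clearly how Grade 3 skin events are to be handled, the risk of inconsistent practice is smaller, but the 4.3.4 line would still need to agree with 4.3.5.

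**What to change.** Change the skin bullet in 4.3.4 only. Keep its present words, "Any grade ≥ 3 skin drug related adverse event", and add after them: *interrupt and apply 4.3.5; resume under 4.3.6 only if nivolumab-only continuation has been approved under 4.3.5.* This relaxes no stop, keeps the nivolumab-only route, and gives the bullet a function.

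Do not add a general sentence barring resumption after any 4.3.5 criterion. A Grade 3 endocrine event not yet stable on hormone replacement meets 4.3.5 at onset, while 4.3.6 lets hormone replacement open the way to retreatment with nivolumab. A general bar would close that route and change handling well beyond skin.

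If the clinical team in fact intends Grade 3 skin events to be held and resumed, it should write that exception into the 4.3.5 criterion by amendment.

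The recommended change costs one reworded bullet in the next amendment and a note to sites. The alternative may cost more: if it is judged to increase potential risk, Protocol 9.1.1 requires a revised consent form, IRB/IEC review and renewed consent from affected subjects. Neither option changes the sample size or any planned analysis.
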